5.2 Recording of Adverse Events

At each contact with the subject, the investigator will seek information on adverse events by specific questioning, reviewing the adverse events diary card, and, as appropriate, by examination. Information on all AEs will be recorded immediately in the source document and the appropriate AE module of the case report form (CRF). All clearly related signs, symptoms, and abnormal diagnostic procedures results will be recorded in the source document.

All AEs occurring during the study period will be recorded. The clinical course of each event will be followed until resolution, stabilization, or until it has been determined that the study treatment or participation is not the cause. AEs still unresolved at the conclusion of the study will be followed up on for one month. SAEs still ongoing at the end of the study period will be followed up to determine the final outcome. Any SAE that occurs after the study period and is

considered to be possibly related to the study treatment or study participation will be recorded and reported immediately.

Expected adverse events include:

- Events associated with venipunctures.
 - Discomfort and slight bruising.
- Events associated with dietary modification.
 - Changes in bowel habits, including diarrhea and/or constipation

Possible, although unlikely, adverse events that may be encountered include:

- Events associated with venipunctures.
 - Bruising
 - Bleeding
 - Lightheadedness, fainting
 - Infection at the venipuncture site
 - Nausea
 - Anxiety
 - Swelling at the venipuncture site

5.3 Adverse Event Management

If an adverse event occurs that requires clinical management, the subject will be evaluated at an unscheduled study visit with a physical exam. Tests and treatments that may be clinically indicated will be ordered.

5.4 Reporting of Serious Adverse Events

5.4.1 IRB Notification by Sponsor Investigator

Reports of all serious adverse events (including follow-up information) must be submitted to the IRB within the reporting timeline requirements, if the SAE falls under the UPIRTSO guidelines. Copies of each report and documentation of IRB notification and receipt will be kept in the Clinical Investigator's binder.

5.4.2 UPIRTSO Events

Upon first learning of a UPIRTSO event, investigators are required to submit a report of the applicable event(s) to the IRB within the required reporting timeline.

5.5 Temporary Interruption of Intervention in an Individual Subject

If a participant does not or cannot comply with the assigned diet intervention, further eligibility will be assessed by the Principal Investigator. A participant may be able to continue in the study if the interruption is temporary (1-2 days).

6 STATISTICAL CONSIDERATIONS

6.1 Sample Size Considerations

This feasibility study plans to enroll 17 participants who will be assigned to receive two dietary interventions in a random order. We anticipate that 2 subjects may drop out from the study for various reasons, including inability to comply with the study visit schedule or new medical

IRB#: 1610M97841

problems unrelated to the study, e.g., use of antibiotics for an infection. The intention of this study is to generate data which will inform the sample size necessary for a larger trial, so power calculations have not been performed.

We will compare primary, secondary, and exploratory outcome measures within each intervention (Day 0 vs. Day 7) and between the two interventions (High-S vs. Low-S) using paired *t*-tests.

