UPIRTSO	Unanticipated Problems Involving Risks to Subjects or Others

PROTOCOL SUMMARY

Title:	Dietary Impact on Intestinal Sulfate Metabolism
Phase:	1
Population:	30 healthy male and female volunteers. Subjects will be recruited from the Twin Cities metropolitan area and will participate as outpatients in this study.
Number of Sites:	1 (University of Minnesota)
Study Duration:	12 months
Subject Participation Duration:	Approximately 1 month
Agent or Intervention:	Dietary intervention will consist of following diets high in sulfur-containing amino acids (SAAs) and low in SAAs for 7 days each, with a 14-day washout period between interventions
Objectives:	The primary objectives of this proposal are to: 1) Compare low sulfur and high sulfur diets with respect to fecal production of hydrogen sulfide (H_2S) and other end products of microbial fermentation; and 2) Determine whether the diet alters the fecal microbiota and the relative proportion of fecal sulfate reducing bacteria.
Endpoints:	The primary endpoint is the change in H_2S concentration measured by gas chromatography. Comparisons will be made between the baseline measurement (Day 0) and end of intervention (Day 7) for each diet (within-group comparison) and between high- and low-sulfur diet H_2S concentration on Day 7 (between group comparison).

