The long-term goal of our research group is to develop evidence-based nutritional strategies for UC that compliment medical therapies. Our strategy is to link specific diets to their effects on microbiota functionality. Nevertheless, we understand that even when armed with the new powerful tools, identifying an effective diet that is also acceptable to patients will be a challenging and resource intensive journey. Therefore, in this proposal, which is our first step toward that ultimate goal, we will test dietary extremes in highly motivated, healthy volunteers. This will allow us to streamline our experimental toolkit and measure the magnitude of the potential effects on gut microbiota composition and function that can be achieved by controlling the diet, which will help to estimate the size of a formal clinical study in patients with UC.

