3.3.1 Tolerability and Feasibility

There are many difficulties associated with examining the effects of dietary components on health, and subject compliance is of major importance to the outcome of any dietary trial. It is extremely difficult to control for subject compliance completely; however, daily diet records during each intervention and 3-day diet records in each standard diet phase, coupled with frequent contact by study staff, will improve participant adherence.

Participants will be provided with a study log at the baseline clinic visit (Day 0). Data recorded in the study log will be reviewed by study investigators at each contact with participants and will be recorded for data analysis. Participants will be instructed to record the following during each day of the study period:

- Adverse events, with specific attention paid to gastrointestinal symptoms including bloating, gas, abdominal pain, constipation, and loose stools
- New medications and/or any medication use – dose and frequency of administration
- Time of bowel movements and stool consistency
- Physical activity

Since the intention of this project is to generate pilot data for a longer randomized trial, approximating compliance for a prolonged period of time (≥ 3 months) is necessary for the design of future interventions. A questionnaire will be developed to assess participants' input on tolerability and feasibility for each dietary intervention.

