4.5 Visit 3 (Day 14 ± 2 days)

- Vital signs
- Weight
- Collection of blood samples for clinical labs and research measurements
- Collection of stool sample for research measurements
- 24-hour urine sample content collection
- Review of 3-day diet record with dietitian
- Review of adverse events and concomitant medications

4.6 Visit 4 (Day 21 ± 2 days; First day of second diet intervention)

- Vital signs
- Weight
- Collection of blood samples for clinical labs
- Collection of stool sample for research measurements
- Assignment of second intervention diet, to begin immediately after conclusion of visit
- Review of 3-day diet record with dietitian
- Review of adverse events and concomitant medications
- Urine collection kit provided, to be completed prior to visit 5

4.7 Visit 5 (Day 28 ± 2 days; Final day of second diet intervention)

- Vital signs
- Weight
- Collection of blood samples for clinical labs and research measurements
- Collection of stool sample for research measurements
- 24-hour urine sample content collection

- Review of 3-day diet record with dietitian
- Review of adverse events and concomitant medications

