6.2 Randomization

This is a randomized, open-label crossover study. Each participant will receive both dietary interventions. The sequence in which participants receive the interventions will be determined through computer-generated random number assignment prepared by the study statistician.

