7.4 Protocol Deviations

A protocol deviation is any noncompliance with the clinical trial protocol. The noncompliance may be either on the part of the subject, the investigator, or the study site staff. As a result of deviations, corrective actions are to be developed by the site and implemented promptly.

When a deviation from the protocol is necessary for an individual subject, the Investigator must complete a description of the deviation from the protocol and justification on the Protocol Deviation Form. It will not be considered a protocol deviation if a subject is unable to provide a stool sample at any visit that requires a stool sample.

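### The between-diet paired t-test has no period term: for outcomes compared as end-of-diet levels, a common period shift inflates the within-person SD and, with unequal sequences, moves the estimate

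*Combined protocol and SAP*

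**What the plan says.** Section 6.1 holds the only analysis statement. It covers all three tiers of outcome and compares them "within each intervention (Day 0 vs. Day 7) and between the two interventions (High-S vs. Low-S) using paired *t*-tests". No section names a period term, a sequence term, a mixed model or a crossover analysis of variance.

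The Protocol Summary defines the between-diet contrast for the primary endpoint as one of levels, "between high- and low-sulfur diet H_2S concentration on Day 7 (between group comparison". Day 7 here means the end of each diet. By sections 4.4 and 4.7 that is study Day 7 for the first diet and study Day 28 for the second: "Visit 5 (Day 28 ± 2 days; Final day of second diet intervention".

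Sections 3.8 and 6.2 say the order is "determined through computer-generated random number assignment prepared by the study statistician". They give no ratio or blocking, and exclude neither. Section 6.1 expects 2 of 17 participants to drop out. Section 7.4 adds: "It will not be considered a protocol deviation if a subject is unable to provide a stool sample at any visit".

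On purpose, section 6.1 says: "The intention of this study is to generate data which will inform the sample size necessary for a larger trial". Sections 1 and 3.3.1 point the same way: "which will help to estimate the size of a formal clinical study in patients with UC" and "the intention of this project is to generate pilot data for a longer randomized trial".

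**The concern.** In a two-period crossover, each participant's High-S minus Low-S difference carries any period effect with a sign set by the order of diets. A paired t-test ignores that order. A shift common to everyone then spreads the two sequence groups apart, and the test reads the spread as within-person noise. If one sequence supplies more pairs, part of the shift also stays in the mean difference.

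The diet difference and its SD are among the main quantities a pilot can hand on. An SD inflated this way is wrong in one direction, and more participants do not cure it. The order of diets is recorded for everyone, so the information needed to remove the effect is already there.

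**Working it through.** **Inputs.** From the documents: the test (6.1); the H2S level contrast (Protocol Summary); samples on Days 7 and 28 (4.4, 4.7); and N, given as 15 (section 3), 17 less 2 dropouts = 15 (6.1) and 30 (Protocol Summary). Both 15 and 30 are used. The documents give no alpha, effect, SD or period shift, and no power calculation to reproduce. Two-sided 5% tests are assumed. All shifts and effects are assumptions, in units of the SD of the within-person diet difference.

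**Model.** d = δ + P·s + e, with SD(e) = 1; s = +1 for Low-S first and −1 for High-S first; P = period 2 minus period 1; n1 and n2 are the numbers in the two sequences.

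**1. SD from the paired test.** Given the split, E(SD²) = 1 + 4·n1·n2·P²/(n(n−1)). Averaged over unrestricted assignment this is 1 + P²:
- P = 0.25: √1.0625 = 1.03
- P = 0.5: √1.25 = 1.12
- P = 1: √2 = 1.41

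Balance does not help. At 15:15 and P = 0.5, the value is 1 + 900 × 0.25/870 = 1.259, and √1.259 = 1.12.

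For scale, sampling error alone gives the SD a 95% interval of 0.80 to 1.34 times the estimate at n = 30 and 0.73 to 1.58 at n = 15.

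**2. Movement of the estimate.** This is P(n1 − n2)/n. At P = 0.5:
- 8:7 gives 0.5 × 1/15 = 0.03
- 10:5 gives 0.5 × 5/15 = 0.17
- 15:15 gives 0
- 18:12 gives 0.5 × 6/30 = 0.10

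The standard error without a shift is 1/√15 = 0.26 or 1/√30 = 0.18. If assignment were unrestricted, a split of 10:5 or worse would have probability 0.30 at n = 15, and 19:11 or worse 0.20 at n = 30. Starting from 15:15, an assumed 10% or 20% loss of pairs leaves the sequences differing by 3 or more with probability 0.12 or 0.25.

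**3. Power, paired / period-adjusted** (200,000 simulated trials per cell, unrestricted assignment):

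| Shift | N = 30, effect 0.55 | N = 15, effect 0.8 |
|---|---|---|
| 0 | 0.83 / 0.82 | 0.82 / 0.79 |
| 0.25 | 0.81 / 0.82 | 0.80 / 0.79 |
| 0.5 | 0.74 / 0.82 | 0.73 / 0.79 |
| 1 | 0.54 / 0.82 | 0.52 / 0.79 |

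The two methods break even at a shift of about 0.2 SD (N = 30) or 0.3 SD (N = 15).

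**4. Type I error at N = 30.** Averaged over assignment, the paired test gives 5.0%. Given the split, at shifts 0.25, 0.5 and 1, it is about 4%, 3% and 0.6% at 15:15, and about 6%, 7% and 9% at 19:11. With the period term it is 4.9 to 5.1% throughout.

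**5. Outcomes analysed as change.** If P is added at both the start and the end of period 2, then (end + P) − (start + P) = end − start. The shift cancels, and only a period difference in the change itself remains.

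**The case against.** The strongest reply is that no shift has been shown. Participants are healthy, eat their usual diet before each period, and give the two end-of-diet samples 21 days apart. The population was raised by amendment to 15, 20 and then 30 between May 2019 and February 2020. If entry was staggered accordingly, calendar effects would not readily line up as one common shift. This stands: every harm figure above rests on an assumed shift, and 1 SD is an extreme. It does not exclude a shift tied to time in the study rather than to the calendar.

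The remedy can also lose. With no shift, or one below break-even, the plain test is slightly better. That stands, but the loss is small beside 8 points (0.82 − 0.74) or 28 points (0.82 − 0.54) at N = 30 for shifts of 0.5 or 1.

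A reader might infer that every outcome is exposed. The documents do not support that. Section 2.5 words bacterial composition, symptoms, bile acids and serum metabolites as changes. If each is taken from its own period's baseline, a level shift cancels. H2S is not rescued, because its between-diet contrast is of levels.

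A reader might also infer that the sequences will be unequal. The protocol is silent on blocking, which does not show that none is used, and it gives no rate of missing samples. Unequal numbers are possible (dropouts are expected, and a total of 15 cannot split evenly) but not established. The SD inflation needs no imbalance.

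Finally, a period-adjusted SD could be computed later from the same data. That is true, and it limits the harm, but section 6.1 does not plan it.

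**Conclusion.** The point holds as a cheap improvement. For end-of-diet levels, above all H2S, the planned between-diet test puts any common period shift into the SD and, with unequal sequences, into the realised estimate. Both results are algebra. Their size here is unknown because the documents give no shift. At 0.25 SD the effect is slight (SD up 3%). At 0.5 SD it is moderate (SD up 12%, about 6 to 8 power points lost against the adjusted model). Inflation of up to 12% lies within the sampling error of the SD, though it always acts upward.

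Two stronger readings fail. The first is that the plan has a false-positive or bias problem. It does not: averaged over randomisation the paired test is unbiased with about 5% type I error, and the departures in either direction are conditional on the split.

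The second is that the later trial will be oversized. Sections 1 and 3.3.1 describe a longer randomised trial in ulcerative colitis without saying that it is a crossover or that this SD will size it; a parallel-group trial would not be sized on it. Only a period-adjusted crossover sized on this SD would grow. With an assumed effect of 0.4 SD and 90% power, it would go from 68 to 72, 85 or 134 participants at the three shifts.

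**What to change.** In section 6.1, replace the between-diet part of the analysis sentence with:

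> Between-diet comparisons (High-S vs Low-S) of the continuous primary, secondary and exploratory outcomes now assigned a paired t-test will use a linear model with participant (fixed), diet and period. Equivalently, the within-person difference will be regressed on sequence coded +1/−1, the intercept being the diet effect. For H2S the end-of-diet values (study Days 7 and 28) will be compared, and the estimate, 95% CI and period-adjusted SD of the within-person difference will be reported.

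That SD is √2 times the residual SD of the participant-level model, or the residual SD of the regression on sequence. The wording covers all the continuous outcomes so that none is left without a between-diet analysis. The within-diet paired comparisons stay as written.

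The change needs no new data and leaves randomisation alone. It costs one degree of freedom and, with unequal sequences, some precision. With no shift the loss is about 1.5 power points at N = 30 and 3.5 at N = 15, with intervals about 2% and 5% wider. The period term does not remove unequal carry-over; nor does the paired t-test. Whether to use pre-diet values is a separate trade-off and is not part of this change.

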6.2 Randomization

This is a randomized, open-label crossover study. Each participant will receive both dietary interventions. The sequence in which participants receive the interventions will be determined through computer-generated random number assignment prepared by the study statistician.

6.3 Blinding

The clinical co-investigators will remain blinded to the intervention. Due to the nature of the intervention, the PI and other personnel giving dietary instructions, and participants will not be blinded. All investigators will be blinded to the randomization schedule and measured endpoints.

6.4 Planned Interim Analyses

Independent monitoring of the clinical study for compliance will be conducted periodically (at a minimum of every 6 months) by qualified staff of the University of Minnesota in accordance with the established monitoring plan. No interim analyses are planned for this study.

6.5 Safety Review

To minimize risk, cumulative safety data will be reviewed by the sponsor-investigator and an independent medical monitor. Medical monitoring will be initiated by the occurrence of adverse events as they arise. This safety monitoring will include careful assessment and appropriate reporting of AEs as noted above. Medical monitoring will include a regular assessment of the number and type of SAEs. Study enrollment and dosing will be stopped and an ad hoc review will be performed if any of the following occurs:

1. Occurrence of a life-threatening allergic/hypersensitivity reaction (anaphylaxis), manifested by bronchospasm with or without urticaria or angioedema;
2. An overall pattern of symptomatic, clinical, or laboratory events that the sponsor-investigator, scientific liaisons, regulatory affairs manager and statistician consider associated with the intervention and that may appear minor in terms of individual events but that, collectively, may represent a serious potential concern for safety;
3. Any SAE that is possibly, probably, or definitely related to the intervention;
4. Two or more subjects experience the same CTCAE Grade 3 or higher adverse event that is possibly, probably, or definitely related to study product administration.

7 DATA AND RECORD KEEPING

7.1 Data Capture Methods

Data for this study will include safety, laboratory and outcome measures. Clinical data (including AEs and concomitant medications) and clinical laboratory data will be managed by the principal IRB#: 1610M97841

investigator, co-investigators, study coordinator, and biostatistician. Data will be entered into REDCap, an internet data entry system provided by the Clinical and Translational Science Institute. The data system includes password protection and internal quality checks to identify data that appear inconsistent, incomplete, or inaccurate. Clinical data will be entered directly from the source documents.

7.2 Source Documents

A source document is defined as the location where study-related data are initially recorded. Source documents for this study will include hard copy paper and/or electronic forms, laboratory printouts, and medical records onto or into which data will first be recorded.

7.3 Study Records Retention

Per University of Minnesota policy all documents concerning the use of human subjects in research will be maintained for at least 3 years from completion of IRB-related work and at least 6 years for HIPAA. No record will be destroyed without the written consent of the sponsor-investigator.

The sponsor-investigator will permit authorized representatives of the University of Minnesota and regulatory agencies to examine (and when required by applicable law, copy) clinical records for the purposes of clinical site monitoring, quality assurance reviews, audits, and evaluation of the study safety and progress.

7.4 Protocol Deviations

A protocol deviation is any noncompliance with the clinical trial protocol. The noncompliance may be either on the part of the subject, the investigator, or the study site staff. As a result of deviations, corrective actions are to be developed by the site and implemented promptly.

When a deviation from the protocol is necessary for an individual subject, the Investigator must complete a description of the deviation from the protocol and justification on the Protocol Deviation Form. It will not be considered a protocol deviation if a subject is unable to provide a stool sample at any visit that requires a stool sample.

8 QUALITY CONTROL AND QUALITY ASSURANCER

8.1 Dietary Intake

Agreement of participants' short- and long-term dietary intake will be assessed through comparison between NDSR and DHQ databases at baseline and Visit 6.

9 ETHICS/PROTECTION OF HUMAN SUBJECTS

9.1 Ethical Standard

The investigator(s) will ensure that this study is conducted in conformity with the principles of The Belmont Report: Ethical Principles and Guidelines for the Protection of Human Participants of Research of The National Commission for the Protection of Human Participants of Biomedical and Behavioral Research (April 18, 1979) and codified in 45 CFR 46, 21 CFR 312,

and/or ICH E6; 62 Federal Regulations 25691 (1997). The University of Minnesota holds a current federal-wide assurance (FWA) issued by OHRP for federally funded research.

9.2 Institutional Review Board

The Human Participants Protection Program at the University of Minnesota will be asked to review and approve this protocol, associated consent documents, and recruitment materials. Approval of any amendments to the protocol or consent materials will also be requested before they are implemented.

